### 9.3.1.1 Timing of Exposure Assessment

#### *Estimated date of last menstrual period (LMP)*

For the calculation of LMP, the following approach will be implemented for all types of pregnancy outcomes, including spontaneous abortion, stillbirth, and live birth.

For the identified end of pregnancy episode, LMP estimation will be based on identifying certain pregnancy-related diagnosis and/or procedure codes and in particular Z3A.® (Z3A), an ICD-10-CM set of codes that indicate weeks of gestation of pregnancy, with the last 2 characters corresponding to specific weeks of gestation. Even though the Z3A codes are not billable codes, insurance providers, *such as Anthem Blue Cross Blue Shield*, are requiring the reporting of Z3A codes for childbirth delivery claims and especially for early elective procedures ([Jamal-Allial et al, 2019](#)). The Z3A code category may serve to more accurately estimate the timing of the pregnancy using administrative claims data. Z3A codes have to be reported alongside the primary pregnancy/delivery code of interest. Because these codes are specific to each week of pregnancy, LMP estimation will be based on the indicated number of weeks of gestation for that reported Z3A code, and an approximate mid-point will be applied, ie, 4 days to each period ([Suarez, 2018](#)).

When Z3A codes are not available, weeks of gestation for LMP estimation will be inferred using an algorithm that is informed by algorithms reported in the literature and refined clinical input will be utilized to estimate the corresponding EDC ([Hornbrook et al, 2007](#); [Margulis et al, 2013](#); [Margulis et al, 2015](#); [Mines et al, 2014](#); [Ailes et al, 2016](#)). The algorithms reported in the literature assume different lengths of gestation for the different pregnancy outcomes, such as full-term singleton births (40-39 weeks), multiples births (36-40 weeks), stillbirths (20-38 weeks), spontaneous abortions ( 20 weeks), and ectopic pregnancies (8 weeks). Recognizing these algorithms may over- or underestimate the true gestational age, other codes that indicate weeks of gestation (eg, HCPCS S2260, *induced abortion, 17-24 weeks*) or the trimester of pregnancy (eg, ICD-10 O09.612, *supervision of young primigravida, second trimester*) will be explored. For codes that are associated with a range of gestational age, an approximate mid-point of gestational weeks 4 days will be assigned based on the reported pregnancy-term code, eg, HCPCS S2260: *induced abortion, 17 to 24 weeks*, so the assigned GA is 20.5 weeks 4 days will be used for EDC estimation. Additional details on validation will be provided in the Statistical Analysis Plan (SAP) and the Medical Record Plan (MRP).

### *End of pregnancy*

Pregnancy end will be defined by the date of delivery for live births and non-live outcomes; and by date of admission with an abortive outcome for pregnancies ending in an abortive outcome.

### *Multiple pregnancies*

To adjust for multiple overlapping pregnancy episodes (eg, a spontaneous abortion claim followed by a live birth claim three days later), once a pregnancy outcome is flagged, there will be a standard 15-day period following the pregnancy outcome where no claims will be assessed (eg a subsequent live birth claim will be ignored). See [Appendix C](#) for windows to assess pregnancy episodes. Additionally, a fixed window between subsequent pregnancies based on the first and subsequent outcomes will be applied, regardless if it is a live or non-live outcome ([Hornbrook et al, 2007](#)). If there are multiple spontaneous abortion or stillbirth events in proximity to one another, the end of pregnancy (EOP) date will be determined using the hierarchy defined below:

1. MarketScan indicators (ED, birthing center, ambulance); not available in HIRD
2. End of Pregnancy (EOP) Procedure Codes (ICD-10-CM & CPT)
3. DRG codes defining EOP
4. Other Procedure codes indicating EOP
5. Other Diagnosis codes defining EOP

In the event of non-live and live pregnancy claims reported on the same date, the non-live outcomes take priority over the live birth claims (unless there is indication of multiple fetuses). If a spontaneous abortion claim occurs on the same date as the stillbirth claim, the stillbirth claim will take precedence. In such cases, a hierarchy is required to select the most relevant claim for any given pregnancy episode.

Subsequent live pregnancy outcomes will be assessed in this manner: apply a specific gap period for preterm and post-term pregnancies (using ICD-10-CM specific diagnosis codes), and a 280-day gap (normal pregnancy duration) preceding any full term live pregnancy outcome to avoid overlapping episodes. The 280-day gap or ICD-10-CM specific gap also applies in the event of the last live pregnancy event occurring during the baseline period. In this case, a gap period is necessary to evaluate the first pregnancy episode. Given that the live pregnancy gap period should be similar to the pregnancy period for the live birth outcome, we would not expect to miss capturing any

non-live birth outcomes during this period. Any non-live birth outcomes occurring during this time period should be noted, but not counted in the analysis.

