### **9.8.1 Internal Validity of Study Design**

#### **9.8.1.1 Measurement Error(s)/Misclassification(s)**

The algorithm used for identification of pregnancy episodes and outcomes for pregnancies that end in live births is very robust (99% agreement between algorithm and chart review). However, ascertainment of LMP and gestational age for pregnancies ending in spontaneous abortion or stillbirth is challenging. We will use a previously published method, such as Hornbrook et. Al. to estimate gestational age and LMP.

As with any observational study conducted within the context of an insurance claims database, drug exposure and timing of exposure is never entirely certain. Although there is evidence in the claims of patients receiving a prescription dispensing at an outpatient pharmacy, we are unable to verify that patients actually used the medication.

Conversely, pregnant patients may take pills during pregnancy that were obtained from a prescription written and dispensed prior to the conception date. In addition, the prescription database lacks information on non-reimbursable (over-the-counter) analgesics, medication dispensed during hospital admissions, or obtained from the doctor's office as samples.

The completeness and/or sensitivity of some of the covariates of interest, such as body mass index, alcohol, tobacco and substance abuse, and previous history of congenital malformations, may be low, and residual confounding due to these characteristics may still be present.

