**Appendix C. Minimum Number of Weeks Required to Identify Separate Pregnancy Episodes**

	→First Outcome										
Second Outcome ↓	LB	SB	LB & SB	Ectopic	Tropho- blastic dx	Spontaneou s abortion	Induced abortion	Abortion, type unknown	LB or SB	Early loss, outcome unknown	LB, SB, or Abortion
LB	24	24	24	22	22	20	20	20	24	20	20
SB	24	24	24	22	22	20	20	20	24	20	20
LB & SB	24	24	24	22	22	20	20	20	24	20	20
Ectopic	10	10	10	8*	8	6	6	6	10	6	6
Tropho-blastic dx	10	10	10	8	Review	6	6	6	10	Review*	6
Spont. abortion	10	10	10	8	8	6	6	6	10	6	6
Induced abortion	10	10	10	8	8	6	6	6	10	6	6
Abortion, type unknown	10	10	10	8	8	6	6	6	10	6	6
LB or SB	24	24	24	22	22	20	20	20	24	20	20
Early loss, outcome type unknown	10	10	10	8*	Review	6	6	6	10	Review*	6
LB, SB, or Abortion	10	10	10	8	8	6	6	6	10	6	6

\* Review if 12 weeks

Source: [Hornbrook et al, 2007](https://onlinelibrary.wiley.com/doi/abs/10.1111/j.1475-6773.2006.00635.x), supplemental information. <https://onlinelibrary.wiley.com/doi/abs/10.1111/j.1475-6773.2006.00635.x>

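### The 15-day and 280-day episode rules classify a loss claim shortly before a term live birth in opposite ways, and no order is given

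*Protocol*

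**What the plan says.** All three rules are in the protocol, Section 9.3.1.1, under Multiple pregnancies.

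- **15-day rule.** After any flagged outcome there is a "15-day period following the pregnancy outcome where no claims will be assessed (eg a subsequent live birth claim will be ignored"). The case it is written for is "a spontaneous abortion claim followed by a live birth claim three days later", and there the live-birth claim is disregarded.
- **Same-date rule.** When live and non-live claims share a date, "the non-live outcomes take priority over the live birth claims (unless there is indication of multiple fetuses").
- **280-day rule.** For later live outcomes there is "a 280-day gap (normal pregnancy duration) preceding any full term live pregnancy outcome to avoid overlapping episodes", with a code-specific gap for preterm and post-term births. Of losses inside the gap it says: "Any non-live birth outcomes occurring during this time period should be noted, but not counted in the analysis".

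Appendix C ("Minimum Number of Weeks Required to Identify Separate Pregnancy Episodes") asks for 20 weeks between a spontaneous abortion and a later live birth, and 24 weeks between a stillbirth and a later live birth. The infant cohort in Section 9.2.2.1 is built from live delivery records of the eligible mothers.

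**The concern.** The subsection gives two answers for one pair of claims. Under the 15-day rule the pregnancy is a spontaneous abortion. Under the 280-day rule, if the birth is full term, it is a live birth and the loss is not counted. Two programmers, or the teams working on the two databases, could follow the text faithfully and classify the same woman differently.

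If the 15-day rule prevails, a genuine term birth is counted as a spontaneous abortion. Its infant can then fall out of the denominators for malformations (primary) and small-for-gestational-age (secondary). Pregnancy timing can also move. Where no Z3A code exists, Section 9.3.1.1 falls back on outcome-specific gestational lengths. The median for spontaneous abortion is 10.0 weeks in Table 1 (Method 1), against 39-40 weeks for a full-term singleton. The estimated LMP would then shift by about 29-30 weeks, less the days between the claims, and the 112-day exposure window would shift with it.

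The exception for multiple fetuses is attached only to the same-date rule. A live co-twin whose claim falls one day after a loss claim has no stated protection.

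**Working it through.** **1. The rules side by side.** Let d be the number of days from a loss claim to a full-term live-birth claim.

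| d | 15-day or same-date rule | 280-day rule |
|---|---|---|
| 0 | Loss kept unless multiple fetuses are indicated | Silent: the gap precedes the birth |
| 1-15 (including the protocol's d = 3) | Loss kept, live birth ignored | Live birth kept, loss not counted |
| 16-280 | Silent | Live birth kept, loss not counted |

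The results are opposite on all 15 days from d = 1 to d = 15. Appendix C does not settle this. At these distances it says the claims are not separate episodes (under 20 × 7 = 140 days, or 24 × 7 = 168 days), but not which claim survives.

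**2. Which result is wrong in substance.** The protocol defines spontaneous abortion as a loss before 20 weeks and takes full term as 39-40 weeks. The shortest distance between the two is 39 − 20 = 19 weeks = 133 days. A genuine term birth 1-15 days after the loss claim therefore means that, in a singleton pregnancy, the loss claim is miscoded or misdated.

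**3. The sample-size figure, reproduced for context.** Inputs from Section 9.5: 3% background prevalence, relative risk 2.00 (so 6%), 1:4 matching, 80% power. A two-sided 5% level is my assumption; the protocol gives 95% intervals but no test level.

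n = [1.96·√(p̄q̄·1.25) + 0.8416·√(p₁q₁ + p₂q₂/4)]² / (p₁ − p₂)², with p̄ = (0.06 + 4 × 0.03)/5 = 0.036

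= (0.4082 + 0.2124)² / 0.03² ≈ 428, against 425 in Table 2.

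Power at 425 exposed infants: z = (0.03·√425 − 0.4082)/0.2523 = 0.833, or 79.8%.

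**4. Size.** The protocol does not say how often a loss claim falls just before a live birth, so x, the share of live births affected, is an assumption. With 1,450 exposed pregnancies (midpoint of 1,400-1,500), 62% live births and 77% linkage: 1,450 × 0.62 = 899 live births and 899 × 0.77 = 692 linked infants.

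| x (assumed) | Births recorded as losses (899x) | Linked infants lost (692x) |
|---|---|---|
| 0.1% | 0.9 | 0.7 |
| 0.5% | 4.5 | 3.5 |
| 1% | 9.0 | 6.9 |
| 2% | 18.0 | 13.8 |

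At x = 2%, 425 × 0.98 = 416.5 exposed infants (comparators reduced in proportion) gives z = (0.03·√416.5 − 0.4082)/0.2523 = 0.809, or 79.1% power.

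**The case against.** The best defence is one of scope and sequence. The 280-day paragraph opens by speaking of subsequent live outcomes. If the rules run in the order written, a live-birth claim on day 3 is never assessed, so it opens no gap and nothing clashes. The protocol also says it does not expect to miss non-live outcomes through the gap. Errors that remain are partly covered by record validation of spontaneous abortion, stillbirth and LMP (Section 9.3.4.1) and by quantitative bias analysis (Section 9.6.2.5.3).

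Part of this stands: a stated order would remove the contradiction. But none is stated, the 15-day example is itself a subsequent live birth, and the gap is said to precede any full-term one. Running the 15-day rule first also fixes in place the result that step 2 shows to be wrong. Validation is confined to the HIRD, with about 60% record retrieval, so it cannot correct MarketScan.

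Three stronger inferences are tempting but not supported:

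- **That the same-date rule also contradicts the 280-day rule.** The gap precedes the birth, so at d = 0 the tension is one of principle, not of text.
- **That stillbirth comparisons are materially diluted.** Suppose 0.2-1.0% of live births carried a stray stillbirth code and background stillbirth were 0.6% (both assumptions). False stillbirths would be 0.124-0.62 per 100 pregnancies, and a true relative risk of 2.0 would appear as (1.2 + 0.124)/(0.6 + 0.124) = 1.83 down to (1.2 + 0.62)/(0.6 + 0.62) = 1.49. That implies a predictive value of 0.6/0.724 = 83% down to 0.6/1.22 = 49%. Section 9.3.4 cites 99-100% for published stillbirth algorithms; at 99% the ratio would be 1.99. The 15-day example also concerns spontaneous abortion, and in a stillbirth/live-birth pair the live-birth code may be the wrong one.
- **That the plan ranks live-birth identification as its most reliable element.** Section 9.8.1.1 says identification for "pregnancies that end in live births is very robust (99% agreement between algorithm and chart review"), but makes no such ranking.

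**Conclusion.** The point holds for a spontaneous abortion claim 1-15 days before a full-term live birth. The protocol classifies that pair in two opposite ways, gives no order, and under one of the two records a false loss whenever the birth is genuine and the pregnancy is a singleton. This is a faulty stated rule, not detail left for the analysis plan.

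Its size is unknown. Under assumed shares of 0.1-2% of live births, roughly 1 to 18 exposed pregnancies in MarketScan would change category, and the effect on power for malformations is probably small. Nothing in the protocol shows that the error would differ by exposure. The case for change rests on correct outcome classification and reproducible coding across two databases. It should be corrected, but it does not threaten the study.

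**What to change.** State one precedence in Section 9.3.1.1:

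- A live birth confirmed by a linked infant record or a live-born-specific outcome code overrides a spontaneous abortion claim in the preceding 15 days. A delivery procedure or DRG code alone should not be enough, because such codes can also mark the end of a non-live pregnancy. The code route is needed because only about 77% of infants link in MarketScan.
- Extend the multiple-fetus exception to the 15-day window.
- Send stillbirth/live-birth pairs to a stated tie-break based on the linked infant record, and say what happens when no infant links.
- Report the number of conflicting pairs by cohort and database.
- Keep the current 15-day rule as a sensitivity analysis.

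The cost is one rule in the episode algorithm, one count table and one re-run. No new data are needed.

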###### *Secondary:*

Pregnancies ending in spontaneous abortion, defined as spontaneous losses before 20 weeks of gestation, and identified using ICD-10-CM diagnosis and procedure codes.

Pregnancies ending in stillbirth, defined as *in utero* fetal deaths 20 weeks of gestation and after, and identified using ICD-10-CM diagnosis and procedure codes.

Small-for-gestational age in live-born infants, defined as birth weight 10th percentile, and identified using ICD-10-CM diagnosis codes.

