### **9.3 Variables**

#### **9.3.1 Exposure Assessment**

Pregnant women who have pharmacy claims for erenumab-aooe (identified using NDC codes) in the 112 days prior to the LMP date (to allow for the half-life of erenumab) or during the pregnancy will be considered exposed to erenumab-aooe.

Exposure to erenumab-aooe will be categorized by dose (70 mg versus 140 mg), by length of exposure, and by timing in relation to trimester of pregnancy: before the last menstrual period (LMP, in the 112 days prior to the EDC, this is the exposure window of interest for major malformations), during the first trimester (from the LMP to 90 days after the LMP), during the second trimester (from day 91 after the LMP to day 180 after the LMP), and during the third trimester (from day 181 after the LMP to the end of pregnancy) (see [Section 9.3.1.1](#) for definitions of LMP).

For the comparator cohorts, comparator group A will include pregnant women with migraine who do not have pharmacy claims for erenumab-aooe in the 112 days prior to the LMP but do have evidence of the use of other preventive migraine medications. Comparator group B will include pregnant women with migraine who do not have pharmacy claims for erenumab-aooe or other anti-CGRP medications 112 days prior to the LMP date or during pregnancy

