#### **9.3.2.2 Secondary outcomes**

Spontaneous abortion is defined as loss of the embryo or fetus between conception and the point at which the death would be considered a stillbirth, at week 20 or later ([Likis et al, 2013](#)). In the MarketScan CCE database and the HIRD, spontaneous abortion will be identified through ICD-10-CM diagnostic codes and procedure codes (see [Appendix E](#) for codes).

Stillbirth is generally defined as intrauterine fetal death on or after the 20th week of gestation, of a fetus weighing 350 grams or more ([Likis et al, 2013](#)). Although the date of fetal death may not be known, stillbirth is more likely than spontaneous

abortion to be medically attended, and will be identified through ICD-10-CM diagnostic codes and procedure codes in the MarketScan CCE database and the HIRD (see [Appendix F](#) for codes).

Small-for-gestational age in live born (LB) infants, defined as birth weight 10th percentile, will be identified using ICD-10-CM codes in the MarketScan CCE database and the HIRD (see [Appendix G](#) for codes).

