## Appendix B. Feasibility Assessment and Comparison of Methods for Timing of Exposure Assessment During Pregnancy

Administrative databases can be useful in the assessment of prenatal drug exposure, and estimation of the LMP date is necessary to classify exposure. Incorrect gestational age information can lead to misclassification of medication exposure during specific periods of pregnancy. Since there are no definitive diagnosis codes that clearly indicate the last menstrual period, pregnancy duration, or gestational age, diagnosis and other procedure codes have been recommended and utilized to determine the last menstrual period (LMP). Approaches to arrive at the LMP in patients with live birth outcomes have been thoroughly studied in administrative claims data and have been shown to accurately identify most of these pregnancies ([Ailes EC et al, 2016](#); [Margulis AV et al, 2015](#); [Naleway et al, 2013](#)); however, there is no validated approach for pregnancies ending in non-live outcomes.

We previously tested the feasibility of three approaches in the MarketScan CCE databases to identify the LMP among pregnancies resulting in fetal death ([Hornbrook et al, 2007](#); [Kharbanda et al, 2012](#); [Glaxo SmithKline 2017](#)). To test the first approach ([Hornbrook et al, 2007](#)), we assigned outcome-specific gestational age estimates based on national averages from the literature ([Martin et al, 2003](#); [Copper et al, 1994](#)). Assigning a fixed estimate (eg, patients with stillbirths were assigned a gestational period of 28 weeks) yielded no variability in the gestational age assignment among patients with identical outcomes, which did not accurately reflect the true date of the LMP. However, the approach provided solutions to address pregnancy durations that were incompatible with the respective pregnancy outcomes, overlapping pregnancy episodes, and subsequent pregnancy episodes, which are described in more detail in [Section 9.3.1.1](#)).

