O03.88	Urinary tract infection following complete or unspecified spontaneous abortion
O03.89	Complete or unspecified spontaneous abortion with other complications
O03.9	Complete or unspecified spontaneous abortion without complication
O02.1	Missed abortion
59820	Treatment of missed abortion, completed surgically; first trimester
59812	Treatment of incomplete abortion, any trimester, completed surgically
59821	Treatment of missed abortion, completed surgically; second trimester
59830	Treatment of septic abortion, completed surgically

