**Appendix F. ICD-10-CM and CPT Procedure Codes to Identify Outcomes: Stillbirth**

ICD-10-CM diagnosis or CPT procedure codes	Description of codes
O36.4	Maternal care for intrauterine death
Z37.1	Single stillbirth
Z37.3	Twins, one live born and one stillborn
Z37.4	Twins, both stillborn
Z37.6	Other multiple births, some live born
Z37.7	Other multiple births, all stillborn

**Appendix G. ICD-10-CM and CPT Procedure Codes to Identify Outcomes:  
Small-for-gestational age**

ICD-10-CM diagnosis or CPT procedure codes	Description of codes
P05.1x	Newborn small for gestational age
P05.x	Newborn light for gestational age
P07.0x	Extremely low birth weight newborn
P07.1x	Other low birth weight newborn

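### Spontaneous abortion and stillbirth are defined by a 20-week cut, but same-date conflicts always go to stillbirth, even when a gestational-age code shows an earlier loss

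*Protocol*

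**What the plan says.** The Abstract (secondary outcome variables) describes spontaneous abortion as "defined as spontaneous losses before 20 weeks of gestation, and identified using ICD-10-CM diagnosis and procedure codes" and stillbirth as "fetal deaths 20 weeks of gestation and after, and identified using ICD-10-CM diagnosis and procedure codes". Section 9.3.2.2 repeats the cut: "Stillbirth is generally defined as intrauterine fetal death on or after the 20th week of gestation". It then sends the reader to the code lists in Appendices E and F for identification.

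Section 9.3.1.1, under Multiple pregnancies, gives the rule for conflicts: "If a spontaneous abortion claim occurs on the same date as the stillbirth claim, the stillbirth claim will take precedence".

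The same section takes the LMP from the week in the Z3A code when there is one. Otherwise it infers gestational age from an algorithm with outcome-dependent pregnancy lengths, and says that other codes giving a week or trimester will be explored. Section 9.3.4 proposes an approach resembling one with outcome-specific gestational ages. Appendix B describes the feasibility test of that approach, in which "patients with stillbirths were assigned a gestational period of 28 weeks". It adds that the approach deals with durations that do not fit the outcome, and refers to Section 9.3.1.1 for the details.

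**The concern.** The definition and the operational rule can give different answers for the same loss. The definition asks how far the pregnancy had gone; the rule asks only which codes are present. When the two conflict on one date, the rule always picks the later-gestation outcome, even if the week of gestation is coded on the claim and has already been extracted to date the LMP.

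Two things are at stake. First, the stillbirth count, a named safety outcome, may include losses that the protocol defines as spontaneous abortions. Second, where gestational age has to be inferred from the outcome, a wrong label also produces a wrong LMP. The LMP fixes the exposure window (9.3.1), the baseline period (9.2.4), matching (9.2.3) and eligibility (9.2.2.1). Exposure status would then depend partly on how the outcome was labelled.

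**Working it through.** **Step 1. Does any step apply the 20-week cut?**

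- Definitions (Abstract, 9.3.2.2): split at 20 weeks.
- Appendix F: one stillbirth entry is O36.4, "Maternal care for intrauterine death", listed with no gestational limit.
- Appendix E: spontaneous abortion includes CPT 59821, "Treatment of missed abortion, completed surgically; second trimester", and CPT 59812, which covers any trimester. Section 9.3.1 sets the second trimester as "from day 91 after the LMP to day 180 after the LMP". That is 91/7 = 13.0 to 180/7 = 25.7 weeks, which straddles week 20.
- Section 9.3.1.1: the conflict rule, the hierarchy for dating the end of pregnancy and the gap windows between episodes contain no comparison with 20 weeks. The reconciliation that Appendix B points to is not there.

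So the code lists do not enforce the cut, and labels can cross it in either direction.

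**Step 2. Same-date conflict with a Z3A code.** Take a loss with both outcome codes on one date and Z3A at 12 weeks. By definition it is a spontaneous abortion, since 12 < 20. By the rule it is a stillbirth. The LMP still comes from the coded week, so it is not displaced. The error is in the label only.

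**Step 3. Same-date conflict with no gestational-age code.** Here the label can set the LMP. Inputs: the Method 1 medians in Table 1 (10.0 weeks for spontaneous abortion, 28.0 for stillbirth; Appendix B confirms the 28) and the 112-day window in 9.3.1.

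- Gap between assignments: 28.0 − 10.0 = 18.0 weeks; 18 × 7 = 126 days, which exceeds 112.
- Exposure look-back from the end of pregnancy = 7 × assigned weeks + 112 days.
  - Labelled spontaneous abortion: 70 + 112 = 182 days.
  - Labelled stillbirth: 196 + 112 = 308 days.
- Fills 183 to 308 days before the loss count as exposure under one label and not under the other.

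The 18 weeks is the distance between two assigned values, not a maximum error. True losses at 6, 8, 12, 16 or 19 weeks that are assigned 28 weeks would be displaced by 22, 20, 16, 12 or 9 weeks. Because the fallback takes gestational age from the label, a later check of one against the other could not detect the error.

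**Step 4. Can the bias be sized?** If false stillbirths are equally frequent in both groups, the observed relative risk is 1 + PPV × (true relative risk − 1), with PPV that of the reference group. With the low end of the cited PPV, 0.99, and a true value of 2.0, this gives 1 + 0.99 = 1.99. Going further needs a stillbirth risk s, a spontaneous abortion risk a and a relabelled fraction f, none of which the protocol gives. Assumed values show how open the answer is:

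| s | a | f | PPV = s/(s + a·f) | Observed for true 2.0 |
|---|---|---|---|---|
| 1% | 10% | 0.1% | 0.0100/0.0101 = 0.99 | 1.99 |
| 0.3% | 20% | 2% | 0.003/0.007 = 0.43 | 1.43 |

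The range runs from negligible to serious and depends entirely on the assumptions, so it supports no particular size.

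**The case against.** The strongest reply is that the documents give no sign that this happens often. Section 9.3.4 cites stillbirth PPVs of 99-100%, and the frequency of same-date dual claims is not reported. Records for spontaneous abortion, stillbirth and LMP will be sought (9.3.4.1), quantitative bias analyses will be explored (9.6.2.5.3), and coding detail may sit in the SAP or the Medical Record Plan. The outcomes are secondary, with comparisons made only if sample size and overlap suffice.

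Much of this stands and limits the point. Three stronger readings should be resisted:

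- *Early losses demonstrably fill the stillbirth count.* A reader might infer this from the rule, but the documents show a risk, not an occurrence. The cited PPVs point the other way, although they come from published algorithms and not from this code list with this tie-break.
- *Every conflict displaces the LMP by up to 18 weeks.* It does not where a Z3A code exists, and other week or trimester codes may help where it does not. The 28 weeks is a feasibility-test value that Appendix B itself criticises, and Section 9.3.4 commits only to a similar approach.
- *Table 1 shows mislabelled losses.* The stillbirth minimum of 5.9 weeks is identical under all three methods. It cannot be a measured age under Method 1, which assigned a fixed 28 weeks, so truncation at another episode is a plausible cause. The spontaneous abortions reaching 30.0 weeks come from Method 2, which was not chosen and whose timing assumptions Appendix B found did not hold in MarketScan.

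What does not stand is the suggestion that this is detail left for later. The protocol itself states the conflict rule, and that rule gives a label contrary to the definition. Validation is confined to the HIRD, with record retrieval of about 60%. Nothing says that its results will correct labels in MarketScan.

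**Conclusion.** The point holds as an internal contradiction. The outcomes are defined at 20 weeks, the stated conflict rule ignores gestational age, and a loss with both codes and a Z3A code below 20 weeks would be labelled against the definition. This conclusion needs no assumed rate.

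The effect on the LMP is conditional. It arises only where no Z3A or other usable gestational-age code exists and an outcome-specific fallback is used. With the feasibility-test assignments the displacement between labels is about 18 weeks (126 days), more than the 112-day window.

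The resulting bias in the stillbirth or spontaneous abortion comparison is unknown. At the cited PPV it would be negligible. The primary outcome, malformations in live-born infants, is untouched by this rule. The change is worth making because it is cheap and brings the rule into line with the definition, not because a large error has been shown.

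**What to change.** In Section 9.3.1.1, replace the same-date rule with:

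> If spontaneous abortion and stillbirth claims occur on the same date, the loss is classified by the Z3A or other gestational-age code on the end-of-pregnancy claim (<20 weeks spontaneous abortion, >=20 weeks stillbirth). If there is no such code, the stillbirth claim takes precedence in the main analysis, and a sensitivity analysis reclassifies these losses as spontaneous abortion, with LMP re-estimated.

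Also report, by database and cohort, the number of losses whose outcome code and gestational-age code disagree at 20 weeks, whether or not there is a same-date conflict. That count would show whether the problem matters in practice. Correct Appendix B so that its reference to Section 9.3.1.1 leads to this rule.

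The cost is one programming rule using codes already extracted for LMP, one sensitivity run and one table. The downside is that a few losses may change category wrongly, either because Z3A is miscoded or because the death preceded the coded procedure date; Section 9.3.2.2 itself notes that the date of fetal death may be unknown.
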